- d **In case of premature permanent IMP discontinuation**, patients should have a visit as soon as possible with the assessments normally planned in V28 or V35 for randomized treatment or extension period, respectively (the 2-hour standardized meal test is performed only if the patient receives the IMP on the day of the meal test). Afterwards, the patients should continue in the study up to the scheduled date of study completion. They should be followed up according to the study procedures as specified in the protocol (except for the 3 day safety post-treatment follow-up). **In case of rescue therapy**, all assessments planned in V28 or V35 for randomized treatment or extension period, respectively should be performed before starting rescue therapy, patients then continue the study treatment (including metformin \pm pioglitazone \pm SGLT2 inhibitor), and all visits and assessments should be performed as scheduled.
- e These additional titration phone calls are necessary only in the fixed ratio combination (FRC) arms during the first 8 weeks of treatment, from V3 (Week 0) to V19 (Week 8), hereafter, from V19 (Week 8) until V28 (Week 26), the dose will be adjusted as necessary to maintain this fasting SMPG target, with recommendation to evaluate the dose at least once a week. Please see [Section 8.1.4.1](#) on dose adjustment.
- f Whenever the patient feels hypoglycemic symptoms, plasma glucose should be measured by the patient (or others, if applicable), if possible. Patients should be instructed to measure plasma glucose levels prior to the administration of glucose or carbohydrate intake whenever symptomatic hypoglycemia is suspected, unless safety considerations necessitate immediate glucose/carbohydrate rescue prior to confirmation.
- g The training can be repeated as often as necessary.
- h The 7-point SMPG profile should be measured at the following 7 points: pre-prandial and 2 hours postprandial for breakfast, lunch, dinner and at bedtime.
- i Any patient treated with a **once weekly GLP-1 RA** upon entering the study who is assigned to receive FRC treatment should not receive their first dose until at least 1 week after their last dose of GLP-1 RA. For these patients baseline visit must be scheduled at least 1 week after administering their last dose of GLP1.

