- j At V2 and V28 and V35, FPG and C-peptide are part of the standardized meal test. The standardized meal contains approximately 600 kcal and is composed of 50 to 55% carbohydrate, 15 to 20% protein and 25 to 30% fat. The standardized meal for all patients should be consumed within a 15-minute period.
- k LDL = low density lipoprotein, HDL = high density lipoprotein.
- l Screening urinalysis at V1: (pH, glucose, ketones, leucocytes, blood/hemoglobin, protein), Urinalysis at V2 (Albumin/creatinine ratio (1st morning urines)

- m* FSH = follicle stimulating hormone.
- n* Safety Laboratory: hematology = White blood cell count (WBC), Red blood cell count (RBC), Hemoglobin, Hematocrit, platelets, differential blood count (Neutrophils, lymphocytes, monocytes, eosinophils, basophils). Serum chemistry = total bilirubin, AST, ALT, alkaline phosphatase (ALP), creatinine, uric acid, sodium, potassium, phosphorus, calcium.
- o* Samples for antibody assessment to be taken prior to IMP injection.
- p* Total plasma concentrations of lixisenatide for patients on FRC will be assessed in the time frame from 1 to 4 hours post-injection at Day 1 of the treatment and prior to injection as well as in the time frame from 1 to 4 hours post-injection at other visits. Samples will also be taken in case of premature discontinuation from IMP or in case of rescue therapy initiation, if possible. In case of premature discontinuation, one PK sample is sufficient if the last dose of IMP is not administered at the visit.
- q* At V11 and V21, only samples for anti-lixisenatide antibody assessment.
- r* One additional sample for potential additional assessments of immunogenicity will be taken at Week 26 (if the patient completes the study after Week 26) or Week 52 (if the patient participates in the extension period) or in case of premature discontinuation.

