9.2.1.2.2 Standardized meal test

Patients will undergo a standardized meal challenge to assess fasting and postprandial glucose (central laboratory), as well as plasma glucose excursion at V2 (Week -1) and V28 (Week 26), as well as V35 (Week 52) for patient continuing in the extension period.

The standardized meal contains approximately 600 kcal and is composed of 50 to 55% carbohydrate, 15 to 20% protein and 25 to 30% fat. The composition and the quantity of the standardized meal must be identical throughout the study.

If the patient needs to receive a rescue antidiabetic medication, the standardized meal test should be performed before the introduction of the rescue medication and will not be performed at the final on-treatment visit.

In case of permanent discontinuation of IMP, the standardized meal test should be performed only if the patient receives IMP on the day of the visit for daily IMP, or one to three days after the injection of the weekly GLP1-RA, and will not be repeated at the final on-treatment visit (Week 26 or Week 52).

On the day of the standardized meal test, the patients will come to the investigational site in the morning, in fasting conditions for at least 8 hours (no food or drink during this time except water), before the scheduled standardized meal test. At V28 (Week 26) and V35 (Week 52) injection of

FRC or Byetta® (patients injecting Byetta® before breakfast) should be done at the investigational site 30 minutes before the start of the standardized meal. Patients taking Bydureon®, Tanzeum®, or Trulicity® should inject their medication as per their usual weekly schedule. The meal test should be preferably performed from one to three days after the injection of the weekly GLP1-RA.

The standardized meal for all patients should be consumed within a 15-minute period.

Blood for plasma glucose and C-peptide is drawn 6 times:

- 30 minutes prior to the start of the meal and before IMP administration if done before breakfast;
- Just before the start of the standardized meal (0 minute);
- 30 minutes after the start of the standardized meal;
- 60 minutes after the start of the standardized meal;
- 90 minutes after the start of the standardized meal;
- 120 minutes after the start of the standardized meal.

The exact times of the IMP injection and the standardized meal intake and the blood draws are to be documented.

9.2.1.2.3 *Self-monitored plasma glucose profiles (SMPG) and glucometer*

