The use of balance scales is recommended; if digital scales are used, testing with standard weights is of particular importance. The floor surface on which the scale rests must be hard and should not be carpeted or covered with other soft material. The scale should be balanced with both weights at zero and the balance bar aligned. The patient should stand in the center of the platform as standing off-center may affect measurement. The weights are moved until the beam balances (the arrows are aligned). The weight is read and recorded in the e-CRF and Source Data. Self-reported weights are not acceptable; patients must not read the scales themselves.

9.2.1.2.5 *Dose of IMP*

The patients document daily/weekly their IMP dose(s) or any missed IMP injection(s) in the patient diary.

The following values will be entered in the e-CRF:

- GLP-1 RA (Victoza®, Byetta®, Bydureon®, Tanzeum®, or Trulicity®):
 - During the screening period and at randomization (V3): daily/weekly dose(s);
 - Throughout the treatment period (after V3 until V28): Any dose change(s).
- FRC:
 - From V3 to V19: daily dose and time of injection before breakfast on the day prior to each on site or phone visit;
 - After V19 and during extension period: daily dose. Time of injection to be recorded in case of change of dose;
 - Dose and time of injection on the day prior to PK sampling;
 - Dose and time of injection for any occurrence of hypoglycemia or allergic reaction;
 - Daily dose and time of injection used on the 7-point SMPG days, meal test days, and days of first and last injection of IMP.
- Missed IMP injections and overdose (if applicable);
- In case of any change in doses administered or hypoglycemia (if appropriate), the dose and injection time should be entered in the e-CRF.

9.2.1.2.6 *Fasting plasma glucose*

FPG is measured at a central laboratory. At V2, V28 and V35, FPG will be part of the standardized meal test.

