2.4.4.2 Analyses of secondary efficacy endpoints

For secondary efficacy endpoints included in the multiplicity procedure described in [Section 2.4.4.3](#), 2-sided statistical tests for the superiority of FRC over GLP-1 receptor agonist will be performed at the alpha level of 0.05.

Except for 2-hour PPG and glucose excursion, all continuous secondary efficacy endpoints at Week 26 defined in [Section 2.1.3.2](#) will be analyzed using the same MMRM approach as described in [Section 2.4.4.1](#) to compare FRC with GLP-1 receptor agonist. The analyses include all scheduled measurements collected during the 26-week randomized treatment period, including those obtained after IMP discontinuation or introduction of rescue therapy. This model will include fixed effect terms including treatment group (FRC or GLP-1 receptor agonist), randomization strata of HbA_{1c} (<8%, ≥8%) at V1 (week -2), randomization strata of GLP-1 receptor agonist subtype (QD/BID formulations, QW formulations) at screening, scheduled visit, treatment-by-visit interaction, and world region, and the covariate of baseline value-by-visit interaction. Means and adjusted means of each treatment group will be provided, as well as adjusted mean and associated two-sided 95% CI of the differences between treatment groups. The statistical tests for between-group differences will be two-sided at the alpha level of 0.05.

2-hour PPG and glucose excursion, for which only 1 post-baseline assessment is scheduled, will be analyzed using ANCOVA with the missing data at Week 26 imputed by LOCF to compare FRC with GLP-1 receptor agonist. This model will include fixed effect terms including treatment group (FRC or GLP-1 receptor agonist), randomization strata of HbA_{1c} (<8%, ≥8%) at V1 (week -2), randomization strata of GLP-1 receptor agonist subtype (QD/BID formulations, QW formulations) at screening, and world region, and a covariate using the corresponding baseline value. Means and adjusted means of each treatment group will be provided, as well as adjusted mean and associated two-sided 95% CI of the difference between treatment groups. The LOCF procedure will be used by taking the last available post-baseline measurement collected during the 26-week randomized treatment period as the value at Week 26.

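### The protocol is contradictory on whether FPG is drawn at Week 26 after rescue or IMP discontinuation, because the V28 sample is tied to a meal test these patients do not have

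*Protocol*

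**What the plan says.** **Where the Week 26 sample comes from.** Protocol 9.2.1.2.6 (Fasting plasma glucose) says: "At V2, V28 and V35, FPG will be part of the standardized meal test". Flow-chart footnote j repeats it: "At V2 and V28 and V35, FPG and C-peptide are part of the standardized meal test". In the FPG row of the randomized-period chart, footnote j is attached only to V2 and V28. The other FPG cells (V1, V3, V11, V19, V21, V26) carry a plain mark.

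**Who has no meal test at Week 26.** Under Protocol 9.2.1.2.2, if rescue is needed, "the standardized meal test should be performed before the introduction of the rescue medication and will not be performed at the final on-treatment visit". After permanent IMP discontinuation the test is done at the discontinuation visit only under conditions on IMP timing, and it "will not be repeated at the final on-treatment visit (Week 26 or Week 52".

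**What continues.** Flow-chart footnote d says of rescued patients that they stay on study treatment "and all visits and assessments should be performed as scheduled". Section 8.2.3 says much the same, and 10.3.4 keeps discontinued patients on the study procedures to the scheduled end of the study.

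**How FPG is analysed.** SAP 2.4.4.2 puts the change in FPG into an MMRM on all scheduled values of the randomized period, "including those obtained after IMP discontinuation or introduction of rescue therapy". SAP 2.4.4.3 tests it second among the secondary endpoints, after the proportion reaching HbA1c <7%.

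**The concern.** The SAP commits a confirmatory endpoint to data collected regardless of rescue or discontinuation. The two protocol passages that deal specifically with the Week 26 FPG sample attach it to a procedure that rescued and discontinued patients do not undergo at that visit. No sentence provides for a stand-alone sample when the meal test is omitted. Sites could read this differently. Where the sample is left out, it is left out because of rescue or discontinuation, which are the events the analysis is meant to include.

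The FPG result would then be described as covering post-rescue and post-discontinuation data. At Week 26 it would rest largely on patients still on unrescued treatment, with the others handled by a missing-at-random model. A claim on FPG and the two later steps of the hierarchy depend on that result.

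**Working it through.** The plan gives no figure for FPG to reproduce. Its only sizing (Protocol 11.1, SAP 1.3) is for HbA1c. With the difference diluted to 0.4 × (1 − 0.20) = 0.32, SD 1.1 and two-sided 5%, it reproduces at 250 per group with 90.1% power (noncentral t). That neither supports nor weakens this point.

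**1. The instructions side by side**

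| Points to no V28 FPG | Points to a V28 FPG |
|---|---|
| 9.2.1.2.6 and footnote j: the V28 FPG is a component of the meal test | FPG has its own central-laboratory row, separate from the meal-test row |
| 9.2.1.2.2: no meal test at Week 26 after rescue | Footnote d and 8.2.3: assessments continue after rescue |
| 9.2.1.2.2: meal test not repeated at Week 26 after discontinuation | 10.3.4: study procedures continue after discontinuation |

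The left column is specific to this sample and the right column is general. Neither expressly overrides the other.

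**2. How much other FPG data these patients have.** After baseline, FPG is scheduled at Weeks 4, 8, 12, 22 and 26. Under 8.2.3, rescue needs HbA1c above 8% at Week 12 or later, confirmed on a repeat at the next visit or within 4 weeks. After Week 12 the only scheduled FPG draws are at Weeks 22 and 26, so without V28 a rescued patient has at most one scheduled post-rescue value, at Week 22. A patient whose alert comes from the Week 22 sample has none.

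**3. What fills the gap under SAP 2.5.4.** Target day = 7 × week + 1, as in SAP Table 3. Lower bound = target − int((target − preceding target)/2). Upper bound = target + int((next target − target − 1)/2).

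| Visit | Target day | Window |
|---|---|---|
| Week 4 | 29 | 1 to 29 + int(27/2) = 42 |
| Week 8 | 57 | 57 − 14 = 43 to 57 + 13 = 70 |
| Week 12 | 85 | 85 − 14 = 71 to 85 + int(69/2) = 119 |
| Week 22 | 155 | 155 − int(70/2) = 120 to 155 + 13 = 168 |
| Week 26 | 183 | from 183 − int(28/2) = 169 |

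If the V28 value is absent, a pre-rescue (Visit 6000), early-termination (Visit 7000) or unscheduled (Visit 9900) FPG from day 169 on can become the Week 26 value. After a Week 22 alert the next visit is Week 24, target day 7 × 24 + 1 = 169. The pre-rescue sample of a late-rescued patient can therefore fall in the Week 26 window and stand in for a post-rescue value. Samples before day 169 do not count as Week 26.

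**4. How many patients.** The documents give no rescue rate. If the share rescued or discontinued but still attending V28 is assumed to be 5%, 10% or 20% (the last being the planning drop-out rate), then 0.05 × 500 = 25, 0.10 × 500 = 50 or 0.20 × 500 = 100 patients are exposed to the ambiguity. This counts patients and does not measure bias.

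**The case against.** The strongest reply is that the exemptions name the meal test and not FPG. On that reading footnote j only says how the sample is taken when the test is done. The separate FPG row, footnote d, 8.2.3 and 10.3.4 then mean FPG is still due at V28. At early termination, too, footnote d excepts only the meal test from the V28 assessments. Sampling detail is left to a laboratory manual (Protocol, introduction to section 9) that is not available here and may settle the matter.

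This is a fair reading, and it defeats two stronger conclusions that a reader might draw.

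- **That Week 26 FPG is collected solely within the meal test.** This is an inference. The text supports a conflict, not a stated decision to omit the sample.
- **That these patients have no Week 26 value and drop out of the analysis.** They do not drop out. Their FPG through Week 22 is independent of the meal test and enters the MMRM, and values from day 169 can fill Week 26. The extension chart also marks FPG at V28a, on the same day as V28, without footnote j. That backstop is one-sided, since it serves only FRC patients who qualify for the extension and never a control patient.

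What the reply does not supply is a sentence requiring the sample when the meal test is omitted. A site that gives the specific text precedence over the general text would be acting reasonably.

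**Conclusion.** The point holds as a contradiction in the protocol with a consequence for a confirmatory endpoint. The specific text, followed literally, loses post-rescue and post-discontinuation FPG at V28 that SAP 2.4.4.2 intends to use. The affected Week 26 values would be handled as missing at random or, from day 169 on, replaced by a pre-rescue or early-termination value.

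On direction, the suggested control rescue is basal insulin (8.2.3), which Protocol section 4 describes as acting primarily on fasting hyperglycemia. Losing late post-rescue control values could therefore leave the control mean too high and favour FRC. A reader might go further and attach a number: 5–20% affected and a post-rescue fall of 1–2 mmol/L give 0.05 × 1 = 0.05 to 0.20 × 2 = 0.4 mmol/L. The documents do not support this as an estimate of bias, for four reasons:

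- Both inputs are assumptions.
- The share mixes rescued with discontinued patients, and stopping a GLP-1 RA could move FPG the other way.
- The figure ignores what the MMRM recovers from Week 22.
- Patients rescued after Week 22 have at most about four weeks on rescue by Week 26.

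The net direction and size across both arms cannot be derived. The finding rests on the conflict in the text and does not need the figure.

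**What to change.** Add to Protocol 9.2.1.2.6 and to flow-chart footnote j: *A fasting sample for central-laboratory FPG is drawn in every patient at V28, at V35 and at the early-termination visit, whether or not the standardized meal test is performed.* Carry the same sentence into the laboratory manual.

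The cost is that sentence and one tube. Protocol 10.1 already requires fasting at all on-site visits, and blood is drawn at V28 for HbA1c in any case.

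SAP 2.5.4 needs no change. Its re-allocation rule applies only when the scheduled value is missing, so a V28 FPG, once drawn, cannot be displaced by a Visit 6000 or Visit 7000 value.

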9.2.2 Safety endpoints

The safety endpoints are assessed by:

- Symptomatic hypoglycemia (documented, probable, severe symptomatic hypoglycemia);
- Adverse events (AE), serious adverse events (SAE); adverse event of special interest (AESI), AEs requiring specific monitoring and reporting on specific electronic case report forms (e-CRFs) (suspected allergic reactions, patients with increased pancreatic enzymes >2 ULN/pancreatic events, patients with increased calcitonin ≥ 20 pg/mL, Device-related events (DRE));
- Safety laboratory values;
- Vital signs;
- Electrocardiogram (ECG);
- Immunogenicity (antibody variables, FRC group): anti-insulin and anti-lixisenatide antibodies.

Observation period of safety endpoints

The observation period of safety data will be divided into 3 segments:

- The pre-treatment period is defined as the time between the date of the informed consent and the first injection of open-label IMP;
- The 26-week on-treatment period is defined as follows:
 - For patients who are not eligible to enter the extension period, the 26-week on-treatment period is defined as:
 - For patients receiving daily IMP: time from the first injection of open-label daily IMP up to 3 days (1 day for symptomatic hypoglycemia) after the last injection of daily IMP, regardless of the introduction of rescue therapy;
 - For patients receiving weekly IMP: from the first injection of open-label weekly IMP up to 9 days (7 day for symptomatic hypoglycemia) after the last injection of weekly IMP, regardless of the introduction of rescue therapy.
 - For the patients who are eligible to enter the extension period, on-treatment period is defined as time from the first injection of open-label IMP up to V28/Week 26 visit (or Day 183 if V28/Week 26 visit is missing).
- The on-treatment period for the whole study (including the 26-week extension period) is defined as the time from the first injection of open-label IMP up to 3 days (1 day for symptomatic hypoglycemia) after the last injection of IMP, regardless of the introduction of rescue therapy. For patients who are not eligible to enter the extension period, the on-treatment period for the whole study is the 26-week on-treatment period.
- The post-treatment period is defined as the time starting 4 days (2 days for symptomatic hypoglycemia) after the last injection of open label daily IMP, or starting 10 days (8 days for symptomatic hypoglycemia) after the last injection of open label weekly IMP (after the on-treatment period for the whole study).

The baseline value for safety endpoints will be the last available value prior to the first injection of IMP.

9.2.2.1 Symptomatic hypoglycemia

Symptomatic hypoglycemia (documented, probable, severe symptomatic hypoglycemia) will be assessed. Please refer to [Section 10.6.1](#) for details.

9.2.2.2 Adverse events

AE including SAE and adverse events of special interest (AESI) will be assessed. Please refer to [Section 10.4](#) to [Section 10.7](#) for details.

Adverse event collection: Adverse events and serious adverse events will be collected from the time of informed consent signature and then at each visit until the end of the study.

9.2.2.3 Laboratory safety variables

All laboratory data listed in this section will be measured at a central laboratory. The laboratory data will be collected at designated visits in [Section 1.2](#). Clinical laboratory values will be analyzed after conversion into standard international units. International units will be used in all listings and tables. The conventional unit will be presented if appropriate.

The following laboratory safety variables will be analyzed:

- Hematology: blood count (erythrocytes, hemoglobin, hematocrit, leukocytes), differential blood count (neutrophils, lymphocytes, monocytes, eosinophils, basophils) and platelets;
- Clinical chemistry: total bilirubin (and, in case of values above the normal range, differentiation in conjugated and non-conjugated bilirubin), Aspartate aminotransferase (AST), Alanine aminotransferase (ALT), Alkaline phosphatase (ALP), creatinine, uric acid, sodium, potassium, calcium, phosphorus;
- Lipid parameters (total cholesterol, high density lipoprotein (HDL)-cholesterol, low density lipoprotein (LDL)-cholesterol, triglycerides);
- Serum amylase and lipase;
- Serum calcitonin;
- Urine albumin/creatinine ratio assessment (to be done on first morning urine sample).

In addition, the following laboratory data will also be collected at screening visit, baseline visit and at on-site visits depending on the item (see [Section 1.2](#)) for identifying patients with exclusion criteria, childbearing potential or safety consideration.

- Hepatitis B surface antigen and hepatitis C antibody (only at screening);
- Urinalysis (assayed by the central laboratory): pH, glucose, ketones, leucocytes, blood/hemoglobin, protein (only at screening);
- Serum pregnancy test in females of childbearing potential;
- Serum follicle stimulating hormone (FSH) (only in females requiring confirmation of postmenopausal status, and only at screening).

In case of suspected acute pancreatitis, safety laboratory, including amylase and lipase should be performed in a timely manner. Please also refer to [Section 10.6.4](#).

Notes: Any abnormal laboratory value should be immediately rechecked (whenever possible using the central laboratory) for confirmation before making a decision of permanent discontinuation of IMP for the concerned patient. Please also refer to [Section 10.3](#) and the “General Guidelines for reporting AEs” in [Section 10.4.2](#).

